#### 14.3.5. Mixed Meal Tolerance Test

The MMTT will be performed after an overnight fast, according to [Greenbaum \(2008\)](#) at baseline (within 3 week prior of randomization) and at each subsequent visit at month 6, 12 and 18. MMTT should not be performed within one week of resolution of a diabetic ketoacidosis event, defined as the presence of:

- hyperglycemia (blood glucose >200 mg/dL);
- pH <7.3 or HCO3 <15;
- ketones positive in the serum or urine.

Prior to the test, patients will withhold long-acting insulin on the morning of the test. Rapid-acting and short-acting insulin will be allowed up to 6 hours and 2 hours, respectively, before the test. Test will be re-scheduled if the patient has a capillary glucose value of >200mg/dL or <70mg/dL.

The test will be initiated before 10 a.m. After 2 pre-meal basal samples have been drawn between -20 to 0 min (basal 1 and basal 2), patients will be given 6mL/kg of Boost® High Protein Nutritional Drink (Nestlé Nutrition) up to a maximum of 360mL, to be drunk within 5 min. Post-meal samples will be drawn at 15±5, 30±, 60±10, 90±10, 120±15, 120±15 min after the meal.

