### 2.5.3.3. Mixed Meal Tolerance Test

Participation in the study requires testing for  $\beta$ -cell function through a Mixed Meal Tolerance Test (**MMTT**) to be performed in basal conditions at baseline (pre-dose) and then at the visits at month 6, 12, and 18. This is not a routine test in patients with new onset diabetes, but has become a standard for the purpose of research studies and is performed frequently by investigational sites.

Apart from the risks due to blood samplings detailed above, the MMTT requires an overnight fast that may potentially increase the risk of a hypoglycemic event. However, detailed instruction for patient management provided by the Investigator will minimize the risk of metabolic unbalance.

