### **6.6. CONCOMITANT MEDICATION**

#### **6.6.1. Reporting of prior and concomitant medications**

Administration of all prior (within 1 month before enrolment) and concomitant medications (CMEDs), **apart from insulin** and the agents listed below, will be reported in the appropriate section of the eCRF.

All the details as per the eCRF fields (sequential number, drug name, indication, starting dose, start/stop date, route of administration) will be recorded. Change in dose will be tracked.

The following agents do not need to be recorded: homeopathic medications; elective vitamins and minerals; osmotic laxatives and locally acting antacids; topical medication.

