##### Drugs that affect glucose homeostasis or its readout

- Twice daily pre-mixed insulin
- Metformin, sulfonylureas, glinides, thiazolidinediones, exenatide, liraglutide, DPP-IV inhibitors, SGLT-2 inhibitors or amylin, or any medications known to influence glucose tolerance (e.g.  $\beta$ -blockers, angiotensin-converting enzyme inhibitors, interferons, quinidine antimalarial drugs, lithium, niacin, etc) [off period before randomization = 2 weeks];
- Any immunosuppressive medications, including oral, inhaled or systemically injected steroid, and any other investigational agents, including any agents that impact the immune response or the cytokine system [off period before randomization = 1 month].

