### 11.2. DIARY

A Diary (local language version) will be provided to each patient randomized into the trial.

The patient will report in the Diary the details (date, time, number of capsules) of each administration of the IMP, values of daily SMBG, daily insulin doses, carbohydrates intake at each meal if patient is able to apply carbs counting, hypoglycemia episodes. It is responsibility of the Investigator to explain to each patient how to enter the data in the Diary and to check the data inserted in the Diary to ensure correct completion as well as correct intake of the IMP.

The information collected in the Diary will be part of the patient's eCRF.

Diary is the sole property of Dompé and should not be made available in any form to third parties, except for authorized Dompé designee or representatives of appropriate Health/Regulatory Authorities, without written permission from Dompé.

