## 7.2.1.9 Average (previous 3 days) daily insulin requirement (IU/kg/day)

Average daily insulin requirement (CRF - INSULIN REQUIREMENT form) and its change from baseline will be summarized at each available timepoint and comparison between treatments will be performed by means of two-sample t-test or, if assumptions of normality are not confirmed (by Kolmogorov-Smirnov test), two-sample Mann-Whitney U test.

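### Protocol 14.3.5 allows short-acting insulin until 2 h before the MMTT but rapid-acting only until 6 h; on assumed durations of action, the longer-lasting class gets the shorter gap

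*Protocol*

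**What the plan says.** Protocol 14.3.5 has patients withhold long-acting insulin on the test morning and then states: "Rapid-acting and short-acting insulin will be allowed up to 6 hours and 2 hours, respectively, before the test". The test follows an overnight fast, and "The test will be initiated before 10 a.m". There is one glucose gate: "Test will be re-scheduled if the patient has a capillary glucose value of >200mg/dL or <70mg/dL". Two basal samples are drawn in the 20 minutes before the meal, and post-meal samples run to 120 min.

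No other section bars short-acting insulin. The only insulin on the restricted list in Protocol 6.6.2 is "Twice daily pre-mixed insulin".

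On how the data are used:
- The 2-hour C-peptide AUC is a secondary endpoint at Months 6, 12 and 18 (Protocol 4.1).
- SAP 9.1 (Table 3) takes the average of the two basal samples as the starting value of the AUC.
- SAP 7.2.1.3 compares the AUC and its change from baseline between arms by t-test or Mann-Whitney test. SAP 4.8 rules out formal hypothesis testing.

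On insulin records, Protocol 6.6.1 collects concomitant medication "apart from insulin". The diary in Protocol 11.2 collects "values of daily SMBG, daily insulin doses, carbohydrates intake at each meal". SAP 7.2.1.9 takes the average daily requirement from a dedicated CRF form.

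**The concern.** A wash-out rule before a stimulation test would be expected to ask for a longer gap for insulin that acts longer. If short-acting insulin outlasts rapid-acting insulin, this sentence does the reverse: it is strict for the class that clears sooner and lenient for the class that persists.

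Injected insulin still acting during sampling can lower glucose and so alter the C-peptide response. It also adds some hypoglycemia risk, in a test whose overnight fast Protocol 2.5.3.3 already recognizes as a hypoglycemia risk. What is at stake is the precision and between-visit comparability of the C-peptide AUC, which is the trial's direct measure of β-cell function. Enrolment stopped early, so there is less room for avoidable noise.

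**Working it through.** The plan gives no figure to reproduce. The check is how long a dose taken at its permitted limit could still be acting while samples are drawn. It measures time, not size of effect.

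**Inputs**
- Gap g: 6 h for rapid-acting and 2 h for short-acting (Protocol 14.3.5).
- Sampling window: -20 to +120 min at nominal times, 140 min in all. The basal part belongs in it because the average basal value enters the AUC (SAP 9.1, Table 3).
- Duration of action D: not in the documents. Assumed 3-5 h for rapid-acting and 5-8 h for short-acting.

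**Formula.** With the meal at time 0, action ends at 60(D - g) min. Overlap = max(0, min(120, 60(D - g)) + 20) min.

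| Rule | Class and gap | Assumed D (h) | Overlap (of 140 min) |
|---|---|---|---|
| As written | rapid, 6 h | 3 / 4 / 5 | 0 / 0 / 0 |
| As written | short, 2 h | 5 / 6 / 7 / 8 | 140 / 140 / 140 / 140 |
| Both at 6 h | rapid, 6 h | 3 / 4 / 5 | 0 / 0 / 0 |
| Both at 6 h | short, 6 h | 5 / 6 / 7 / 8 | 0 / 20 / 80 / 140 |
| Numbers swapped | rapid, 2 h | 3 / 4 / 5 | 80 / 140 / 140 |
| Numbers swapped | short, 6 h | 5 / 6 / 7 / 8 | 0 / 20 / 80 / 140 |

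**How much rests on the assumed durations.** At g = 2 h the overlap is the full 140 min once 60(D - 2) ≥ 120, that is, D ≥ 4 h. The inversion itself needs only the ranking, short-acting longer than rapid-acting.

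**Why 6 h for both cannot increase overlap.** The overlap formula never rises as g rises. Moving short-acting from 2 h to 6 h therefore lowers its overlap or leaves it alone, and the rapid-acting rule does not change. At D = 8 h the overlap stays at 140 min. A gap of 8 h would leave 20 min at D = 8 h and none at 7 h or less.

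**Why a plain swap is not clearly better.** Let s be the share of tests preceded by short-acting insulin, the rest preceded by rapid-acting, with every dose at its limit. Mean overlap is 140s as written and r(1 - s) + ws after a swap, where r = 80-140 and w = 0-140. The swap improves on the current rule only if s > r/(140 + r - w). At best (r = 80, w = 0) that is 80/220, or about 36%; at w = 140 it never does. Holding both classes at 6 h gives ws, which is at most 140s for every s.

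**Clock time.** For a test at the 10 a.m. limit, the 2 h gap ends at 8 a.m. and the 6 h gap at 4 a.m. The change affects only short-acting doses taken between 4 and 8 a.m.

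**Is testing already over?** The enrolment-interruption communication is dated 28 March 2022 (SAP 1). If no one consented after it, the maximum 100-day run-in gives a last Day 1 by 6 July 2022. Adding 78 + 2 = 80 weeks gives a last Month 18 test by 17 January 2024, 111 days before SAP v3.0 (7 May 2024).

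**The case against.** The strongest reply is that no harm is shown and the exposure is small. The patient is fasting, so a dose in the 6-to-2-hour interval would mainly be a correction dose. Tests outside 70-200 mg/dL are re-scheduled. Protocol 2.5.3.3 relies on the Investigator: "detailed instruction for patient management provided by the Investigator will minimize the risk of metabolic unbalance". Protocol 7.1.1 adds a call in the two weeks before each planned visit, to settle the insulin to be taken for at least the last three days. The primary endpoint does not use the MMTT. All of this stands and keeps the point minor. It does not remove the point: the glucose gate comes before the test and cannot detect insulin that acts later, and neither the instructions nor the call states an interval.

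It is also fair to say that the inversion rests on pharmacology outside the documents. That is why the durations are labelled as assumptions.

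Three stronger readings are tempting, and the documents support none of them:
- **That the two numbers were transposed.** The same paragraph has other slips (a 30-minute sample with no tolerance, the 120-minute sample listed twice), so this is plausible. The cited MMTT method is not available to confirm it.
- **That the C-peptide comparison is biased.** Both blinded arms follow one rule, so noise is likelier. Bias would need pre-test insulin use to differ by arm.
- **That insulin class and clock time went unrecorded.** The text does not show that they were captured. The forms are not shown either, and diary data become part of the eCRF, so what can be reconstructed is unknown.

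**Conclusion.** The point holds as a minor one. Protocol 14.3.5 gives the shorter gap to the insulin class assumed to last longer, and no other text corrects it. At the permitted limits, short-acting insulin overlaps 140 of 140 min of sampling for any duration of 4 h or more; rapid-acting overlaps 0 min for durations of 3-5 h. These are upper limits on time, for a dose taken exactly at its limit. The number of tests affected and the effect on AUC cannot be computed from the documents. The consequence is confined to the MMTT-based C-peptide summaries, which SAP v3.0 treats as descriptive.

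**What to change.** If any MMTT is still to be done, reword 14.3.5 so that the last dose of either rapid-acting or short-acting insulin is at least 6 h before the test. Relax rapid-acting to 2 h only if the sponsor confirms that the cited MMTT method says so. The cost is one sentence and a site memo. The downside is fewer early-morning corrections, so possibly more tests re-scheduled for glucose above 200 mg/dL.

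If all MMTTs are done, as the dates suggest, rewording changes nothing. Ask sites which interval they applied to each insulin class and state the answer beside the C-peptide AUC results in the study report. The cost is one query and one sentence.

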# PPD

## Abbreviations

ADR	Adverse Drug Reaction
AE	Adverse Event
ATC	Anatomical Therapeutic Chemical
AUC	Area Under the Curve
BDRM	Blind Data Review Meeting
BMI	Body Mass Index
CGM	Continuous Glucose Monitoring
CONGA	Continuous Overall Net Glycemic Action
CS	Clinically Significant
ECG	Electrocardiogram
eCRF	electronic Case Report Form
eGDR	estimated Glucose Disposal Rate
ENR	Enrolled set
FAS	Full Analysis set
HbA1C	Glycated hemoglobin
HLA	Human Leukocyte Antigen Complex
IC	Informed Consent
ICH	International Council for Harmonisation
IMP	Investigational Medicinal Product
IRS	Interactive Response System
ITT	Intent to Treat
MAGE	Mean Amplitude Glycemic Excursions
MAR	Missing at Random
MCMC	Markov chain Monte Carlo
MedDRA	Medical Dictionary for Regulatory Activities
MI	Multiple Imputation
MI-RD	Multiple Imputation using retrieve dropouts
MMRM	Mixed Model for Repeated Measurements
MMTT	Mixed Meal Tolerance Test
MNAR	Missing Not At Random
MODD	Mean Of the Daily Differences
NCS	Not Clinically Significant
CCI	
PP	Per Protocol set
PPG	PostPrandial Glucose

# PPD

PT	Preferred Term
QTcF	corrected QT interval by Fredericia
RND	Randomized set
SAE	Serious Adverse Event
SAF	Safety set
SAP	Statistical Analysis Plan
SAS	Statistical Analysis Systems
SD	Standard Deviation
SE	Standard Error
SI	Standard International
SOC	System Organ Class
T1D	Type 1 Diabetes
TEAE	Treatment Emergent Adverse Event
TESAE	Treatment Emergent Serious Adverse Event
TIR	Time in range
TLF(s)	Tables, Listings and Figures
US	United States
WHO DD	World Health Organization Drug Dictionary

## Revision History

Document Version	Changes Made	Document Date
Final 1.0	First release	CC1
Final 2.0	Section 4.3: Definition of primary estimand;  Section 4.7: Clarification on handling of missing data;  Section 4.8: Description of the main change compared to the planned analysis in the protocol;  Section 7.1.2: Inclusion of the MI-RD as method to handle missing data in the primary analysis.	CC1
Final 3.0	The SAP has been revised considering the premature closure of the study. Efficacy analyses have been reduced in scope given the limited sample size of the study compared to the expected one.	7 May 2024

# PPD

Document Version	Changes Made	Document Date
	
The main sections impacted are:
 

• Section Efficacy endpoints: one single final analysis has been planned after DB lock;

• Section 4.3: removal of the primary estimands;

• Section 4.4 and 4.8: modified to reflect the reduction in the efficacy analyses;

• Section 4.5 and 5.5: given the reduced sample size compared to the planned one, some analyses (subgroup analysis and Kaplan-Meier curve for the time-to-discontinuation analysis) have been removed from the statistical plan;

• Section 7.1 and 7.2: given the reduced sample size compared to the planned one, some advanced analyses (logistic regression, multiple imputation approaches, sensitivity analysis) have been removed from the statistical plan;

• Sections 12.1: clarifications.

• Section 6 regarding Compliance has been updated

• CGM parameters units have been added

• Severe Hypoglycemia derivation has been updated in section 9.1

• Additional information regarding Reason for discontinuation summaries has been added in 5.1 section.

• Additional details regarding stop enrollment and changes in planned analysis has been added

• HLA DR-DQ haplotypes will be only listed

• Section 7.2.1.6 updated

• Details and correction of the Cox model

• Derivation of severe hypoglycemia events has been added

• Number of AEs added in AE summaries

	

# PPD

Document Version	Changes Made	Document Date
	

• Section 6.1.2.2.: ON/OFF Compliance calculation in case of missing start/end cycle dates

• Section 5.6: Difference between first IMP administration and first insulin administration will be calculated

	

# PPD

## 1. Introduction

This document outlines the statistical methods to be implemented in the analysis of the data of LDX0419 Clinical Trial. The purpose of this plan is to provide general guidelines from which the analysis will proceed, containing a more technical and detailed elaboration of the principal features of the analysis described in the protocol. Any changes to the protocol or electronic Case Report Form (eCRF) may necessitate updates to the Statistical Analysis Plan (SAP). In case of deviations from this updated SAP, explanations will be provided in the clinical study report.

The SAP V1.0 and V2.0 were based on study protocol Version No. 1 final – CCI [1] and Version No. 2 final – CCI [2] (for US only).

The present version of the SAP refers to the same versions of the study protocols and includes the updates to the analysis based on the company decision to prematurely stop the enrolment.

More details about this decision are described in the official document “Communication of enrolment interruption” dated 28 March 2022 [3] sent to the sites.

Please refer to section 4.8 for additional details on the changes of the originally planned analysis plan due to the premature closure of the study.

## 2. Study Objectives

The objective of this clinical trial is to assess whether ladarixin treatment is effective to improve glycemic control in newly diagnosed T1D adult patients with preserved  $\beta$ -cell function. The safety of ladarixin in the specific clinical setting will be also evaluated.

## 3. Study Design

### 3.1 General design and plan

[figure not shown]
The study will be a phase 2, multicenter, double-blind, placebo-controlled study. It will involve 75 adults (18-45 years, inclusive) patients with new-onset T1D. Patients will be randomly (2:1) assigned to receive either ladarixin treatment or matched placebo (control group). The two groups will be balanced within centers.

Recruitment will be competitive among the study sites, until the planned number of patients is enrolled.

Each patient will be involved in the study for a run-in period (Screening and Baseline assessments) followed by a randomization visit and a post-randomization period up to 18 months from the 1st IMP

# PPD

dose. The study will proceed under double-blind condition up to the month 12 visit of the last patient randomized. Thereafter, the blind will be broken and remaining follow-up will proceed in an open fashion. This approach will allow to anticipate access to safety and efficacy data without significantly affecting data integrity.

## 3.2 Visit Schedule and Visit Windows

Assessments and study visits will be performed as listed in Table 1. Paragraph no. 7 "Study procedure and assessments" of Study Protocol contains additional details about scheduled visits and time windows.

For all measurements, the actual date and time of assessment, including date of sampling, will be recorded in the eCRF. Time frame for each assessment is reported in the following sections. Month/Week match is detailed below, together with acceptable windows:

- Month 6 = Week 26±2
- Month 12 = Week 52±2
- Month 18 = Week 78±2

Baseline is defined as the last visit prior to randomization. It is scheduled within 3 weeks to start of 1st treatment cycle. Unless otherwise specified, baseline values are defined as the measurements taken during this visit (unscheduled visits will not be considered for the definition of baseline value).

In case of multiple measurements during baseline visit, the last assessment will be considered as baseline evaluation.

# PPD

Table 1: Study Flow Chart

**100 days (run-in phase)**

**1st insulin**

**first IMP dose**

Procedures	Screening	Baseline (within 3 weeks to C1 start)	Randomization (within 3 days of C1)	TREATMENT PERIOD (cycle = C) - 13 Cycles (C1 - C13)								FOLLOW-UP	
				C1 - C3	Week 11 (end of 3 rd cycle)	C4 - C6	Week 23 (end of 6 th cycle)	C7 - C9	Month 6 Week 26±2 Visit while on C7	Week 35 (end of 9 th cycle)	C 10 - C13	Month 12 Week 52±2	
Tests to be performed at a centralized laboratory													
Test to be performed at the local laboratory													
Informed Consent Form	X												
Eligibility criteria Randomization	X	X	X										
Auto-antibodies  & Fasting C-Peptide 	X												
Medical history	X												
BP/HR		X			X		X			X		X	X
weight, height, waist & waist/hip circumference		X							X			X	X
eGDR		X							X			X	X
Insulin requirement previous 3 days		X							X			X	X
Self Reported Severe Hypoglycemia		X							X			X	X
HLA DR-DQ haplotypes, Proinsulin,	X												
HbA1c, CCI		X							X			X	X
Safety Laboratory Test (hematology & biochemistry) 	X			X		X			X			X	X
MMTT 		X							X			X	X
Pregnancy Test	X			X		X			X			X	
12 lead ECG	X			X 		X 			X 			X 	X 
CGM download 	X 								X 			X 	X 
IMP dispensation 		X		X		X				X			
Patient Diary delivery/check		X		X		X				X		X	X
Check discontinuation criteria 				X		X				X			
Patient Phone call 			X	X	X	X	X	X	X	X	X	X	X
AE/SAE recording			X										
Prior and Concomitant Medication			X										

# PPD

 anti-GAD; IAA (if obtained within 10 days of the onset of insulin therapy); IA-2; ZnT8.

 fasting C-peptide must be  $\geq 0.205$  nmol/L on two occasions.

 tests performed at Baseline should be planned to ensure the samples are sent to the laboratory and results are available in time for randomization.

 **sensor to be positioned at least 10 days before the scheduled visits**

(X) CGM sensor implantation can occur at Screening Visit and Week 23 Visit if the visit is scheduled 14-10 days before Baseline and before Week 26 respectively

 Dispensation of IMP (Patient Kits) must occur ONLY after check of inclusion/exclusion criteria (at the Randomization Visit) and of discontinuation criteria (at the Visits performed at the end of the 3rd, 6th, 9th treatment cycles). Results of ALT/AST, bilirubin, creatinine and albumin, ECG reading and pregnancy results **should be made available by the local laboratory in time to allow Patient Kits dispensation as soon as possible during the visit**. If this expedite timing cannot be achieved, Patient Kits might be delivered to patient named address by a selected courier (CRO to support shipment). As per treatment discontinuation criteria, no IMP will be dispensed in the case: QTcF is either  $> 500$  msec or has increased by  $> 60$  msec from baseline measurement on two consecutive ECG readings taken 1 hour apart; the patient develops any significant cardiovascular disease/abnormality, renal (eGFR  $< 60$  mL/min/1.73 m^2) or hepatic (increased ALT/AST  $> 3 \times$  ULN and increased total bilirubin  $> 3$  mg/dL [ $> 51.3$   $\mu$ mol/L]) dysfunction, hypoalbuminemia (serum albumin  $< 3$  g/dL), significant systemic infection that must be assessed on a case-by-case basis by the investigator regarding whether they are serious enough to warrant discontinuation, ketoacidosis or hypoglycemic coma; a female patient has become pregnant.

 Telephone calls will be scheduled on a regular basis to ensure optimization of metabolic control. It is expected that patients are contacted at least every 2 to 3 weeks during study participation. A telephone call will be anyway scheduled in the 2 weeks before a planned visit.

# PPD

### 3.3 Sample size justification

Below, the calculation performed for the sample size at the time of the study planning.

The sample size of the study is calculated on the “proportion of patients with a HbA1c <7% and daily insulin requirement <0.50 IU/Kg/day”, a post-hoc composite endpoint derived from data of the phase 2 trial (CCI [REDACTED]), considering a larger effect size expected from the longer treatment length (one year versus 3 months).

Based on these assumptions, and considering a randomization ratio 2:1 (ladarixin:placebo) and a one-sided alpha of 0.05, seventy-five (75) patients randomized in the trial will allow to achieve a power of approximatively 80% to detect at least 35% of difference in terms of primary endpoint in favour of ladarixin vs placebo, assuming that the proportion of patients in the placebo group with a HbA1c <7% and daily insulin requirement <0.50 IU/Kg/day at 12 months will range between 45% and 55%.

Assuming that 10% of subjects will be not evaluable for primary analysis, a total of approximately 84 subjects is expected to be enrolled.

As reported in section 1, enrolment was prematurely stopped per company decision.

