#### **Statistics**

The sample size of the study is calculated on the "proportion of patients with a HbA1c < 7% and daily insulin requirement <0.50 IU/Kg/day", a post-hoc composite endpoint derived from data of the phase 2 trial CCI [REDACTED], considering a larger effect size expected from the longer treatment length (one year versus 3 months). Based on these assumptions, 75 patients randomized in the trial will allow to achieve a power of approximatively 80% to show superiority of ladarixin vs placebo in terms of primary endpoint, considering a one-sided alpha of 0.05 and a drop-out rate of 10%.

Summary statistics have been defined for quantitative variables (number of observations, mean, standard deviation, median, minimum and maximum) and qualitative variables (number and percentage per category). If appropriate, confidence intervals around the mean or the proportions will be presented.

The proportion of patients with HbA1c < 7% and daily insulin requirement <0.50 IU/Kg/day at Month 12 (primary endpoint) will be analyzed by means of logistic regression.

All secondary endpoints will be analysed at each available timepoint by means of descriptive statistics and by appropriate parametric tests. Change from baseline value and shift tables versus baseline will be summarized for all post-baseline visits.

AEs will be presented in terms of the number of AEs and incidence. Other safety parameters will be summarized by treatment at each available visit by means of descriptive statistics.

The Safety and the Full Analysis Set population will consist of all patients who will be randomized and received at least one dose of the investigational product. Safety population will be analyzed according to the actual treatment received; Full Analysis Set population will be analyzed according to ITT principle, i.e. by treatment allocation. Primary and secondary efficacy analyses will be conducted on the FAS population while the SAF population will be used for safety analyses.

The Statistical Analysis Plan (SAP) will be issued with more technical and detailed elaboration of the principal features of statistical analyses. Any deviation from the original statistical plan will be described in the Clinical Study Report.

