## 9. STATISTICAL ISSUES

### 9.1. SAMPLE SIZE

The sample size of the study is calculated on the “proportion of patients with a HbA1c <7% and daily insulin requirement <0.50 IU/Kg/day”, a post-hoc composite endpoint derived from data of the phase 2 trial [CC1], considering a larger effect size expected from the longer treatment length (one year versus 3 months).

Based on these assumptions, and considering a randomization ratio 2:1 (ladarixin:placebo) and a one-sided alpha of 0.05, seventy- five (75) patients randomized in the trial will allow to achieve a power of approximatively 80% to detect at least 35% of difference in terms of primary endpoint in favor of ladarixin vs placebo, assuming that the proportion of patients in the placebo group with a HbA1c <7% and daily insulin requirement <0.50 IU/Kg/day at 12 months will range between 45% and 55%.

The above sample size will take into account a drop-out rate of approximately 10%.

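### Does the figure of about 84 in SAP section 3.3 contradict the 75 randomised in Protocol section 9.1, and is the stated 80% power wrong?

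*SAP*

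**What the plan says.** Protocol section 9.1 states that 75 "patients randomized in the trial will allow to achieve a power of approximatively 80% to detect at least 35% of difference" between the arms. The inputs are 2:1 allocation, one-sided alpha 0.05 and a placebo response of 45% to 55%. It then adds: "The above sample size will take into account a drop-out rate of approximately 10" per cent. The synopsis agrees, giving the power at 75 randomised while "considering a one-sided alpha of 0.05 and a drop-out rate of 10" per cent.

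SAP section 3.3 opens with "Below, the calculation performed for the sample size at the time of the study planning". It repeats the inputs and the claim that "seventy-five (75) patients randomized in the trial will allow to achieve a power of approximatively 80" per cent, omits the drop-out remark, and ends: "Assuming that 10% of subjects will be not evaluable for primary analysis, a total of approximately 84 subjects is expected to be enrolled". SAP section 3.1 keeps the smaller number: "It will involve 75 adults (18-45 years, inclusive) patients with new-onset T1D", with recruitment "until the planned number of patients is enrolled".

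On the word enrolled, Protocol section 7.1.1 defines enrolment as signature of the consent form. SAP sections 4.2.1 and 4.2.2 define separate Enrolled (consented) and Randomised sets. The analysis planned in Protocol section 9.5.2.1 was logistic regression, with missing outcomes filled in by Copy Reference multiple imputation.

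**The concern.** Two things look wrong.

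First, the same 10% is used in two ways. If 75 already contains the loss, about 67 or 68 patients would have outcomes. If the loss is added on top, 84 are needed to leave about 75. The reason given in the SAP, that patients cannot be evaluated for the primary analysis, describes a loss after randomisation. On that reading 84 would be the number randomised, which contradicts the protocol. SAP section 3.1 does not settle this, because it uses enrolled for the number it has just given as 75.

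Second, a standard large-sample test on the stated inputs gives clearly more than 80% power, and no test is named. A power figure that its own inputs do not reproduce raises the question whether the effect size, the alpha or the sample size was misreported.

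At stake is whether the trial had one clear planned size, and whether that size supported the planned comparison.

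**Working it through.** **Inputs.** From Protocol section 9.1 and SAP section 3.3: one-sided alpha 0.05 (z = 1.645), 50 ladarixin and 25 placebo, placebo rate p0 = 0.45, 0.50 or 0.55, ladarixin rate p1 = p0 + 0.35, loss 10%. Assumptions made here: the loss is equal in both arms and the logistic model is unadjusted.

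**The 84.** 75/(1 - 0.10) = 83.3, rounded up to 84. The SAP figure is reproduced. In the other direction, 75 x 0.9 = 67.5 and 84 x 0.9 = 75.6.

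**Can 84 and 75 both hold?** If 84 is the number consented, 75/84 = 0.893 would be randomised. In the earlier trial, Protocol section 2.4.2 reports 85 consented and 76 randomised, and 76/85 = 0.894. The two numbers fit as consented and randomised.

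**Power, one case by hand.** With p0 = 0.45 and p1 = 0.80:
- Pooled rate: (25 x 0.45 + 50 x 0.80)/75 = 0.683.
- Standard error under the null: sqrt(0.683 x 0.317 x (1/25 + 1/50)) = 0.1139.
- Standard error under the alternative: sqrt(0.45 x 0.55/25 + 0.80 x 0.20/50) = 0.1145.
- Power: Phi((0.35 - 1.645 x 0.1139)/0.1145) = Phi(1.42) = 0.92.

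If all 75 had outcomes, a simple test would therefore give 92%, not 80%.

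**The same case with the planned handling of missing data.** Under Copy Reference, the missing 10% of the ladarixin arm respond at the placebo rate, so p1 becomes 0.9 x 0.80 + 0.1 x 0.45 = 0.765 and the difference becomes 0.315.
- Pooled rate: (25 x 0.45 + 50 x 0.765)/75 = 0.66.
- Standard errors: 0.1160 under the null and 0.1162 under the alternative.
- Without continuity correction: Phi((0.315 - 1.645 x 0.1160)/0.1162) = Phi(1.07) = 0.86.
- With the correction, which subtracts 0.5 x (1/25 + 1/50) = 0.03 from the difference: Phi(0.81) = 0.79.

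**All cases.** These come from exact enumeration of the 2x2 table, except the row marked as simulated.

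| Setting, one-sided 0.05 | p0 = 0.45 | p0 = 0.50 | p0 = 0.55 |
|---|---|---|---|
| Logistic (Wald), 75 with outcomes | 0.922 | 0.939 | 0.962 |
| Logistic (Wald), 67-68 with outcomes | 0.896-0.903 | 0.918-0.925 | 0.941-0.951 |
| Fisher, 67-68 with outcomes | 0.838-0.847 | 0.865-0.869 | 0.898-0.902 |
| Logistic (Wald), 75, Copy Reference dilution | 0.858 | 0.877 | 0.907 |
| Logistic, 75, Copy Reference imputation, simulated (20,000 trials, 50 imputations) | 0.850 | 0.877 | 0.906 |
| Fisher, 75, Copy Reference dilution | 0.786 | 0.812 | 0.843 |
| Continuity-corrected, 75, Copy Reference dilution | 0.802 | 0.829 | 0.864 |
| Logistic (Wald), 84 randomised (56:28), Copy Reference dilution | 0.891 | 0.911 | 0.935 |
| Fisher, 84 randomised (56:28), Copy Reference dilution | 0.843 | 0.864 | 0.891 |

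The stated figure of about 80% appears in the Fisher and continuity-corrected rows at 75 with 10% loss, at the lower placebo rates.

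**Another route to both numbers.** A continuity-corrected calculation at two-sided 0.05, 80% power and p0 = 0.45 needs 24.95 placebo patients. That gives 25:50 = 75, and 75/0.9 then rounds up to 84. This conflicts with the one-sided alpha that both documents state, so it is only a possible explanation.

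**The case for a change.** The strongest case for a change is that SAP section 3.3 claims to record the planning calculation and does not record the one in the protocol. Reading 84 as the number consented does not rescue the sentence, because the loss would then be screen failure, not a lack of evaluable outcomes. Non-evaluability also fits poorly with the design. The Full Analysis Set takes every randomised patient who received a dose, and the protocol imputed missing outcomes, so almost nobody would have dropped out of the primary analysis. If instead 75 was meant as the evaluable number, as in the two-sided route above, the SAP and Protocol section 9.1 conflict directly. A clarification would cost only a few words.

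Much of this stands. The stated reason is out of place, enrolled is used loosely, and the sizing test should have been named.

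Three points limit its weight.
- No contradiction in the numbers is shown, because under the documents' own definition of enrolment both figures can hold.
- The SAP's current missing-data rule (section 4.7) cannot be used against the planning text. Imputation was removed in version 3.0, after recruitment was stopped.
- Nothing says that the trial was sized with its analysis model. A gap between 80% and the logistic-regression figure is therefore not an arithmetic error, and putting a recalculated power into a historical record would misreport what was done.

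**Conclusion.** The 75-versus-84 mismatch is a clerical slip in how the 10% is described. It does not show two different planned sizes: both documents keep 75 randomised, and 84 is readable as the number consented.

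The power statement holds. It is about 79-86% with a one-sided Fisher or continuity-corrected test, and about 85-91% with the planned logistic regression. Both ranges are for 75 randomised with Copy Reference handling, and they assume 10% missing in each arm and no covariate adjustment. The stated 80% is therefore fair or conservative, and 75 was not too small on the stated inputs. Which test was actually used is not documented and cannot be recovered from the text.

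No change follows, because nothing now depends on the answer. SAP section 3.3 marks the passage as the planning calculation and closes by noting that enrolment stopped early. SAP section 4.8 makes every analysis descriptive, without formal hypothesis testing. SAP section 5.1 already reports patients enrolled, enrolled but not randomised, and randomised, so a reader will see the real counts at each step. A clearer sentence would be tidier, but it would alter no patient, data point, analysis or conclusion.
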